7.2.4 OBSERVATION

The site will follow its standard operating procedure (SOP) to monitor postoperative subjects in the recovery room and PACU. The Investigator or qualified designated study personnel will continue monitoring the subject and observe the subject for at least 1 hour but no longer than 6 hours postoperatively. Any observations can be recorded (by using the mark event button on the CM-1500 device), but it is not required as all relevant events will be recorded in the patients medical records as per the SOP of the site. Observations may include but are not limited to indoor temperature of the postoperative recovery room or PACU, time and type of medication delivery, vital sign data (as obtained as part of the sites SOP), and the subject's position. Following/using the site's SOP, should the subject show signs of hemorrhage or a potentially poor outcome, the site will note this in the EMRs including time and date of the observation.

After the observation period is complete, the monitoring session will be stopped, and the electrode array sets will be removed and disposed of. Redacted medical records will be provided to the Sponsor.

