4 CM-1500 (“DEVICE”)

4.1 DEVICE DESCRIPTION

The CM-1500 is a U.S. Food and Drug Administration (FDA) cleared non-invasive monitoring device that simultaneously monitors five (5) parameters of a patient's body.

Parameters include bioelectrical impedance, heart rate, ECG amplitude, PPG amplitude, and skin temperature. A combination of these parameters is represented by a single number known as the Relative Index value. [REDACTED]

[REDACTED] The Relative Index is a unique functionality of the Zynex CM-1500.

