4.2 PRINCIPLES OF OPERATION

The CM-1500 measures bioelectrical impedance (ohms), heart rate (BPM), ECG amplitude, PPG amplitude, and skin temperature (°C). As parameters change, towards indications of fluid change/imbalance, the Relative Index, [REDACTED]

[REDACTED], will compound these changes into a singular value [REDACTED]

When the monitoring session starts, every patient will start with a Relative Index of 100, signifying the combination of physiological parameters is near or at their original baseline values for all five monitored parameters. All parameters are continuously measured and tracked during a monitoring session. ECG and PPG amplitude values are only visible on the Advanced monitoring session display mode, as selected in the Setup screen.

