7.2.3 DEVICE USE/OPERATION

The Investigator or qualified designated study personnel will operate the device by referencing the Instructions for Use (IFU) manual and following the study-specific steps outlined below. Device operation will begin within 15 minutes (but no longer than 1 hour) after the subject's surgery. Sites will not use the device for clinical decisions but instead follow their standard operating procedures for monitoring postoperative subjects.

- S16. Start the monitoring session by pressing "START" on the CM-1500 display monitor/monitoring screen. A message will appear informing the user that the monitoring session is in progress. The device will begin to measure all five (5) parameters.
- S17. As monitoring continues, the display will show ECG and PPG pulse waveforms along with the Relative Index graph over time. [REDACTED]

[REDACTED] The subject should remain in a supine position (with an allowance to be 30 degrees head up) if possible.

- S18. Continue the monitoring session for at least 60 minutes but no longer than 6 hours postoperatively. The device will monitor until "STOP" is pressed on the monitoring screen. Document any observations or adverse events that occur during the monitoring session.

S19. After the monitoring session is stopped, remove the electrode array sets from the subject and dispose of the electrodes per site guidelines.

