12.4 STATISTICAL ANALYSIS PLAN (SAP)

The majority of evaluations pertaining to the performance of the CM-1500 device will examine the behavior the Relative Index value in accordance with subject outcomes and conditions that present following operatory procedures. The SAP however, can include

investigation into individual vital sign parameters that the CM-1500 device (or another source) produces during a subject's recovery.

Analysis of data sets collected from all subjects aim to satisfy the following purposes, included but not limited to:

- Examine, on a case by case review basis, the results produced by the CM-1500 device for relevant subject case results.

- Classify aggregate results by subject outcomes, particularly nominal and hemorrhagic shock/complications, and evaluate the performance of the CM-1500 to indicate either the presence of the presenting complication, or specify the absence of presenting complications.

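### The hemorrhagic class in 12.4 has no definition and may draw on heart rate, which also feeds the Relative Index, so apparent performance may be inflated and no required analysis would show it

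*Combined protocol and SAP*

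**What the plan says.** - **The index.** Section 4.1: "Parameters include bioelectrical impedance, heart rate, ECG amplitude, PPG amplitude, and skin temperature". It continues: "A combination of these parameters is represented by a single number known as the Relative Index value". Section 4.2 repeats the list and adds that each session starts at 100, meaning at or near that subject's own baseline. The weights are not visible; text near the definition is redacted.
- **The hemorrhage record.** Section 7.2.4 has the site make a timed entry in the medical record "should the subject show signs of hemorrhage or a potentially poor outcome", following its SOP. It lists no qualifying signs, thresholds, tests or adjudication.
- **What else is observed.** The same section gives "vital sign data (as obtained as part of the sites SOP") as one of several observations that may be recorded. On marking observations on the device it says "it is not required as all relevant events will be recorded in the patients medical records as per the SOP of the site". Redacted medical records go to the Sponsor.
- **The analysis.** Section 12.4 plans to "Classify aggregate results by subject outcomes, particularly nominal and hemorrhagic shock/complications", and to evaluate how well the device indicates presence or absence of the complication. It permits, but does not require, analysis of individual vital-sign parameters. It names no accuracy measure, threshold or comparator.

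**The concern.** In a diagnostic evaluation the reference should not depend on the ingredients of the test. Here the reference is left to clinical judgement at a bedside where heart rate is watched. If a rising heart rate makes staff more likely to note hemorrhage, and also moves the Relative Index, the two will agree to some extent even if the other four inputs carry no information.

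Keeping the person who classifies outcomes unaware of the index would not remove this, because the common variable reaches the chart through the site's own vital signs.

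At stake is what a favourable result would mean. Section 10.1 calls the study pivotal. Without heart rate alone as a benchmark, a reader could not tell whether the composite adds anything to what the bedside already shows.

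**Working it through.** **1. The plan's own figures.** The plan gives no accuracy target, so there is none to reproduce. The rates in Section 2 are arithmetically right: 18/107 = 16.82% and 68/500 = 13.6%. Early bleeding (under 24 hours) was 4/107 = 3.74% of patients. AUC is used below only as a yardstick; the plan does not name it.

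**2. An index that knows nothing beyond heart rate.** Assumptions, none from the documents:
- The index is the equal-weight sum of five independent standard normal inputs.
- A subject is labelled when ρ × HR + √(1 − ρ²) × noise falls in the top p of subjects.
- p is 3.75% (close to 4/107) or 1%.

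Apparent AUC from simulation of 2,000,000 subjects:

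| ρ | Index, p = 3.75% | Index, p = 1% | HR alone, p = 3.75% | HR alone, p = 1% |
|---|---|---|---|---|
| 0.3 | 0.586 | 0.602 | 0.689 | 0.722 |
| 0.5 | 0.642 | 0.670 | 0.805 | 0.848 |
| 0.7 | 0.697 | 0.732 | 0.903 | 0.939 |
| 1.0 | 0.775 | 0.815 | 1.0 | 1.0 |

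The same index without heart rate stays at about 0.50.

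Hand check at ρ = 0.3, p = 3.75%:
- The index correlates with the label score at r = 0.3/√5 = 0.134.
- The mean label score is 2.180 in labelled and −0.085 in unlabelled subjects, a difference of 2.265.
- The index means therefore differ by 0.134 × 2.265 = 0.304, and the two index variances sum to 1.981.
- AUC ≈ Φ(0.304/√1.981) = Φ(0.216) = 0.585.

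**3. Change from own baseline.** Section 4.2 makes the index relative to the session start, so a subject already tachycardic and stable at START contributes no heart-rate change. As an assumption, let half the variance of heart rate at labelling be present at START. Then r falls from ρ/√5 to ρ/√10. For ρ = 0.3, 0.5, 0.7 and 1.0 the apparent AUC is 0.56, 0.60, 0.64 and 0.70 at p = 3.75%, and 0.57, 0.62, 0.66 and 0.73 at p = 1%. The effect shrinks but remains.

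**4. An index with real signal.** In a second model (1,000,000 subjects per scenario), hemorrhage is a true state with prevalence 3.7%, 13.6% or 16.8%. It shifts each input by 0, 0.5 or 1.0 SD. The label score gives weight w to site heart rate and 1 − w to an independent clinical sign shifted by 2 SD. Site and device heart rate correlate at 1.0 or 0.8.

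| True AUC of index | Apparent, w = 0 | Apparent, w = 0.25, 0.5 or 1 |
|---|---|---|
| 0.50 | 0.50 | 0.54 to 0.77 |
| 0.785 | 0.63 to 0.68 | 0.69 to 0.78 |
| 0.943 | 0.70 to 0.78 | 0.76 to 0.86 |

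With no signal, heart rate in the label raises apparent AUC above the truth. With real signal, apparent AUC stays below the truth throughout, because the label also misclassifies. Putting heart rate in the label usually raises apparent AUC above its w = 0 value, but not always: with the strongest signal, w = 1 and correlation 0.8, it falls slightly, from 0.766 to 0.759 at 13.6% prevalence and from 0.774 to 0.760 at 16.8%.

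**5. Precision.** If 1% to 3.75% of 200 subjects are labelled, there are 2 to about 8 cases. Hanley–McNeil: SE² = [A(1 − A) + (n₁ − 1)(Q₁ − A²) + (n₀ − 1)(Q₂ − A²)]/(n₁n₀), with Q₁ = A/(2 − A) and Q₂ = 2A²/(1 + A).
- For A = 0.65, n₁ = 8, n₀ = 192: SE² = (0.2275 + 7 × 0.0590 + 191 × 0.0896)/1536 = 0.0116, SE = 0.1075, half-width 1.96 × SE = 0.21.
- For n₁ = 2, n₀ = 198: SE is 0.213 and the half-width about 0.41 to 0.42.

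**The case against.** A reader might infer that test and reference share a measurement and that agreement is therefore overstated. The documents do not support that, for these reasons.

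- **Heart rate is never named as a criterion.** In Section 7.2.4 vital signs are one item in an optional list; the sentence on hemorrhage is separate and refers only to the site's SOP, which is not in the documents. That the label draws on heart rate is a possibility the plan leaves open, not something it states.
- **The two readings are distinct.** Section 7.2.3: "Sites will not use the device for clinical decisions but instead follow their standard operating procedures for monitoring postoperative subjects". Site vital signs come from the site's own process, so the overlap is a shared physiological variable, and the index itself is no formal part of the reference. Section 4.3 describes parameter changes as indicative of fluid-volume change, so heart rate moving with bleeding is partly the intended signal.
- **The note in 7.2.4 need not be the only source.** Step S18 also requires observations and adverse events to be documented, the redacted records go to the Sponsor, and 12.4 does not say which source sets the class.
- **A high heart rate does not by construction move the index.** Only change within the session counts.
- **The direction is open.** Inflation from 0.50, and heart rate beating the index, follow from assuming an index with no other information. Step 4 shows that with real signal the net error can be downward.

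All of this stands, and it limits the claim to a risk. It does not answer the remaining point: the class is undefined, nothing keeps heart rate out of it, and the one analysis that would expose the problem is optional. Nor is the primary objective in Section 3.1 a defence. It concerns changes in the index, but 12.4 still plans to evaluate performance against this class.

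**Conclusion.** The concern holds as a risk that the plan neither prevents nor reveals. The documents establish that heart rate feeds the index, that hemorrhage is recorded on unspecified signs under an SOP that also yields vital signs, and that analysis of single parameters is optional.

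The size is unknown. The range 0.59 to 0.82 illustrates an equal-weight index with nothing beyond heart rate. Under the baseline-change assumption it is 0.56 to 0.73. Neither estimates what this trial will show. The true weights, the influence of heart rate on the site's judgement and the event rate are all undocumented; the 3.75% is borrowed from pancreatic surgery over 24 hours, whereas this trial takes any abdominal or pelvic surgery and monitors for at most 6 hours. With perhaps 2 to 8 cases, a few labels prompted by heart rate could dominate the result. The change is worth making before outcomes are classified.

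**What to change.** In Section 12.4:

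1. Define the hemorrhagic class, for analysis, from items in the medical records that are not device inputs: for example hemoglobin fall, transfusion, imaging or endoscopic proof, visible or drain blood loss, or re-intervention for bleeding. State the rule before outcomes are classified.
2. Put subjects labelled on vital-sign changes alone in a separate group, suspected but unconfirmed, and give results with and without them.
3. Require heart rate alone to be reported beside the Relative Index, on the same subjects and time window, descriptively and with confidence intervals. Read the performance of the index against that benchmark.

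This classifies subjects for analysis only and changes no care. The cost is SAP wording and analysis time: the records already go to the Sponsor and the device already measures heart rate. The downsides are fewer confirmed cases, wide intervals (about ±0.21 at 8 cases and ±0.41 at 2, so any gain over heart rate will be poorly estimated) and possibly less favourable apparent accuracy. Some confirmatory tests may themselves be prompted by vital signs, so the link is weakened, not removed.

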7.3 UNANTICIPATED DEVICE EFFECT (UADE)

Unanticipated Adverse Device Effect (UADE) that occurs after informed consent and before completion of the study will be recorded. UADE's may require follow-up contact via study visit, telephone call, or both depending on the nature of the UADE.

7.4 FOLLOW-UP VISIT/CONTACT

In the event of a poor outcome due to the subject's surgery, the Investigator or qualified designated study personnel will perform follow-up contact via telephone call 7(± 5) days after the outcome occurred. The Investigator or study personal will record any follow-up attempts or contact made. Should the outcome not be resolved in 7(± 5) days, follow up might continue until resolved, or the outcome will be notated as unknown upon approval by the Sponsor.

7.5 SUBJECT COMPLETION

A subject has completed the study when all Screening, Visit 1, and, when applicable, follow-up contact is completed and documented.

7.6 SCHEDULE OF EVENTS TABLE

Table 2: Schedule of Events

STUDY PROCEDURE	SCREENING Day 1	VISIT 1 Day 1	FOLLOW UP CONTACT Day 7 (\pm 5)
Informed Consent (waiver of documentation)	X		
Inclusion/Exclusion	X		
Demographics	X		
Medical and Surgical History	X		
Concomitant Medications	X		(X) if applicable
Prepare Device for Use		X	
Prepare Subject for Device Use		X	
Device Operation/Monitoring Session		X	
Observation		X	
Adverse Events Review		X	(X) if applicable
Follow-Up Contact			(X) if applicable

8 STUDY SUPPLIES AND EQUIPMENT

8.1 STUDY SUPPLIES

Study-specific supplies will include alcohol wipes for CM-1500 electrode application(s).

8.2 DEVICE EQUIPMENT

CM-1500, including the display monitor and all component accessories.

8.3 SAFETY EQUIPMENT

No additional study-specific safety equipment will be required for the investigation. The site will follow their postoperative standard operating procedures.

9 DEVICE MANAGEMENT

9.1 UNPACKING AND INSPECTION

It is the responsibility of the Principal Investigator (PI) to ensure that all devices are unpacked and inspected prior to using in any study procedures. Upon arrival, the Investigator will remove the device display monitor and accessories from the shipping container; ensure all device components are received; complete the unpacking and inspection checklist in Appendix A. The study site must inform the Sponsor of any missing or damaged items within seven (7) days. Devices with any missing or damaged items cannot be used and shall be replaced.

9.2 ACCOUNTABILITY

It is the responsibility of the Principal Investigator to ensure all devices are inventoried and accounted for. The Investigator or qualified designated study personnel will record

all information on the Device Accountability logs (Appendix B) and maintain a copy in the Investigator Site Files (ISF).

9.3 STORAGE

The device(s) will be stored at the study center. When not in use, the device(s) will be stored in a secure location (i.e., area with limited access or in a locked cabinet) under appropriate environmental conditions found in the Instructions for Use (IFU) manual.

9.4 DISPENSATION

The device shall only be used under the supervision of the Principal Investigator. Study Personnel shall not use the device on any person not authorized to receive it.

9.5 LABELING

Investigational device(s) will be labeled with the name and place of business of the manufacturer, quantity of contents if applicable, and the statement "CAUTION-Investigational Device. Limited by Federal (U.S.) Law to Investigational Use." In the instance that a production (commercial) device is used, investigational labels will not be applicable, and instead, production labeling will be used.

9.6 CLEANING

The device shall be cleaned before each use. Cleaning procedures will be followed per the Instructions for Use (IFU) manual. The device should always be turned off and disconnected before cleaning. The site will follow site-specific COVID19-related cleaning policies as applicable.

9.7 RETURN

The device(s) shall be returned to the Sponsor after study completion.

10 RISKS & BENEFITS

10.1 RISK DETERMINATION

This investigation is a Pivotal study that is determined to be an non-exempt, non-significant risk investigation. An Investigational Device Exemption (IDE) will be submitted based on this determination. The device will be used as intended and no clinical decisions will be made based off of the information obtained.

10.2 RISKS

The CM-1500 is a Class II, non-invasive, non-significant risk medical device and does not meet the definition of significant risk under 21 CFR 812.3(m). Adverse events related to the investigation will be recorded and analyzed to evaluate their significance. A report will be written on the findings. There may be other risks that are unknown.

10.2.1 RISKS: USING THE DEVICE

- [Possible, Rare] Skin irritation could occur from the electrodes

10.2.2 WARNINGS: CM-1500 DEVICE

- When using the external power supply, this electrical device does not incorporate a power switch to isolate the system from the ac mains. Unplug the power cord of the ac adapter from the ac mains outlet in order to completely disconnect from the main ac power. Ensure that the AC outlet used for the CM-1500 is easily accessible.
- **BURN HAZARD:** Simultaneous connection of a patient to high-frequency surgical equipment or electrocautery may result in burns at the site of the electrodes and possible damage to the CM-1500.
- **BURN HAZARD:** Do not use the CM-1500 or sensors during magnetic resonance (MR) scanning. The induced current could potentially cause burns. The CM-1500 may affect the MR device, and the MR device may affect the accuracy of the CM-1500 parameters and measurements.
- **BURN HAZARD:** Do not use the CM-1500 or sensors during defibrillation.
- **EXPLOSION HAZARD:** Do not use the CM-1500 in the presence of flammable anesthetics or other flammable substances in combination with air, oxygen-enriched environments, or nitrous oxide.
- **ELECTRIC-SHOCK HAZARD:** Do not open the CM-1500 cover. Only a qualified operator may perform maintenance procedures specifically described in the IFU manual. Refer to Zynex for the repair of this equipment.
- **ELECTRIC-SHOCK HAZARD:** Do not open the power adapter. Refer to Zynex for the repair or replacement of this equipment. **ONLY USE AN APPROVED POWER SUPPLY THAT SATISFIES THE Power Supply Specifications!**
- To protect against injury from electric shock, follow these guidelines:
 - Avoid placing the device on surfaces with visible liquid spills.
 - Do not soak or immerse the device in liquids.
 - Use cleanings solution sparingly and only externally on the device

10.2.3 CAUTIONS: CM-1500 DEVICE

- Tissue damage can be caused by an incorrect application or use of a sensor (e.g., fastening the wrist cuff too tightly). Inspect the sensor sites as directed to ensure skin integrity, correct positioning, and adequate adhesion of the sensors and electrodes.
- Do not apply sensors (including electrodes) to broken or damaged skin.
- Do not autoclave, pressure sterilize, or gas sterilize the CM-1500.

- Do not soak or immerse the monitor in any liquid.
- Use the cleaning solution, sparingly. The excessive solution can flow into the monitor and cause damage to internal components.
- Do not touch, press, or rub the display panels with abrasive cleaning compounds, instruments, brushes, rough surface materials, or bring them into contact with anything that could scratch the panel.
- Do not use petroleum-based or acetone solutions or other harsh solvents to clean the CM-1500. These substances degrade the instrument's materials, and instrument failure may result.
- Do not use damaged sensors and electrodes. Do not use a sensor with exposed optical or electrical components.
- Do not immerse sensors in water, solvents, or cleaning solutions (the sensors and connectors are not waterproof). Do not sterilize by irradiation, steam, autoclave, or ethylene oxide.
- Do not use damaged electrode or trunk cables.
- Do not immerse cables in water, solvents, or cleaning solutions. The patient cable connectors are not waterproof. Do not sterilize by irradiation, steam, autoclave, or ethylene oxide.
- Do not attempt to reprocess, recondition, or recycle Zynex sensors, electrodes, wrist straps, or cables as these processes may damage the components, potentially leading to patient harm.

10.2.4 CONTRADICTIONS: CM-1500 DEVICE

- The CM-1500 is contraindicated for use as an apnea monitor.
- The CM-1500 is contraindicated for patients who have undergone amputation of the left upper extremity.
- The CM-1500 is contraindicated for pregnant patients and children.
- The CM-1500 is contraindicated for use in the Magnetic Resonance Imaging (MRI) environment.
- The CM-1500 is contraindicated for Dextrocardia.

10.3 REDUCING RISKS TO A MINIMUM

Every possible effort will be made to reduce the risks to a minimum. Investigators or qualified designated study personnel will be experienced, receive training on the protocol and use of the device. All adverse events will be documented and reported to the Sponsor.

10.4 BENEFITS

This study is for research purposes only. There is no direct benefit to subjects participating in the study. Information from this study may help other people in the future.

